### 4. Design/Procedure

Select one category that most adequately describes your research:

Pilot study that will be an open trial without a control group. There will be no random assignment; all subjects will get the active treatment.

Recruitment. Veterans will be identified in 3 ways: 1.) At JAHVH, Veterans who are diagnosed with PTSD are offered evidence-based psychotherapy; providers who give a Veteran a PTSD diagnosis will offer MERA to Veterans who endorse aggression. If the Veteran agrees, providers can co-sign the research staff on the Veteran’s note in the electronic medical records or call the study staff. 2.) Research staff will examine up to 1000 new referrals for PTSD evidence-based psychotherapy and with the Waivers of HIPPA Authorization and Informed Consent examine their electronic medical

records to see if they may be eligible for the study. If veterans appear to meet study criteria, study staff will send the Veteran a letter and if no opt-out call is received within two weeks, call Veteran and explain the study. 3.) Veterans can self-refer if they see study flyers or hear about the study from other Veterans.

Research staff will conduct a phone screen to estimate if the Veteran will meet inclusion criteria, and if the Veteran appears appropriate for the study, a full assessment will be conducted.

Screening Procedures. Research staff will call referred Veterans two weeks after the initial study letter is sent to Veterans (or after a provider refers them to the study), explain the study, and receive verbal consent to continue the telephone call. Research staff will then conduct a phone screen to assess for PTSD (PC PTSD-5), aggression frequency in the past month (self-reported number of aggressive acts); active suicidal intent; active homicidal intent; history of PE/CPT initiation; and, if the Veteran has an independent aggression rater, s/he will allow the study staff to contact in order to verify aggressive acts. No screening data will be used as study data. For their convenience, Veterans may be seen in person for the screening. Veterans who meet study criteria will be invited to schedule a time to learn about the study and review informed consent forms. Veterans must then meet eligibility criteria based on the pre-training assessment, before being included in the study.

Measures and assessment schedule. All assessments are routinely used within the VA and DoD.

Veterans will be assessed on the following areas:

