- b) The Emotion Regulation Questionnaire (ERQ) is a 10-item self-report measure with 2 factors that assess specific emotion regulation strategies: cognitive reappraisal (changing the way one thinks about a situation) and expressive suppression (not expressing the emotion outwardly but feeling it internally). More effective emotion regulation is indicated by higher cognitive reappraisal scores and lower expressive suppression scores. Internal-consistency estimates (alpha) were .80 for the reappraisal factor and .73 for the suppression factor in a college-student sample, and both were greater than .75 in a Veteran sample. Scoring is based on how well the items describe the individual in the past week, from 1 (strongly disagree) to 7 (strongly agree).
- 7) Aggression.
  - a) The Impulsive Premeditated Aggression Scale (IPAS) is a 30-item self-report measure that assesses impulsive and premeditated aggression. In psychiatric outpatients, Cronbach's alphas were .82 and .77 for premeditated aggression and impulsive aggression, respectively. Scoring is based on how well each item describes an individual's aggressive acts, from 1 (strongly disagree) to 5 (strongly agree). To determine eligibility for the study, the measure will be scored in a categorical method by calculating the total percentage of positive items ("strongly agree" or "agree") for each aggression subscale and classifying the Veteran as either a primarily impulsive or premeditated aggressor, based on which subscale has the highest percentage of positive items. The summed dimensional score for the impulsive aggression subscale will be used to examine pre to posttraining differences in impulsive aggression.
  - b) The Overt Aggression Scale (OAS) is a 17-item self-report measure that assesses frequency of different aggression acts, including verbal and physical aggression against self, other, and objects. Intraclass correlation coefficients of reliability ranged from .89-.99 in 2 adult psychiatric samples. The measure will be adapted for the current study to indicate frequency of each aggressive act over the past week. Aggressive acts will be summed to create a total score.

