If interested in learning how to decrease your aggression and also want to help other Veterans by evaluating the treatment, please call

[name] at [contact] [name], Principal Investigator

Offered by James A. Haley

Veterans Affairs Hospital.

Funded by the Department

of Veteran Affairs'

Consortium to Alleviate PTSD.

IRB# 23884

Payment:

Veterans will not be paid for taking part in the 3-session training. However, they will be compensated for the pre and post-training assessments. After completing the pre-training assessment, each Veteran will receive a \$30.00 by direct deposit to his bank account. If he is eligible for the study based on screening questions and complete the training, he will complete a post-treatment assessment and receive a \$30.00 by direct deposit after the assessment. If you do not have a bank account, you can be paid by check. That is a maximum of \$60.00 if both assessments are completed.

Veterans will receive a Form 1099 from the VA, which is required to process their payments. This form requires that study staff to use whole social security number instead of just the last 4 digits.

Costs: There are no costs associated with the study over and above the costs that would be incurred from standard care or services. For VA patients, there may be co-payment costs for some of the non-research procedures for which the VA may not pay even if these occur while you are participating in this research. Some veterans are required to pay co-payments for medical care and services provided by the VA. These co-payment requirements will continue to apply to medical care and services provided by the VA that are not part of this study and that you would receive as part of your regular medical care.

**5. Sample size:** We request to consent up to 60 participants to account for potential dropouts. We aim for a sample of 30 Veterans. The final goal is to have complete pre- and post-treatment data for 20 participants. Up to 25 participants may need to complete the post-treatment assessment in order not to slow recruitment at the end of the study.

**6. Study Population with Inclusion/Exclusion Criteria:** Veterans enrolled at the Tampa VA and who meet the following criteria will be recruited to the study:

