Inclusion criteria: 1.) Male Veteran who served in OEF/OIF/OND. 2.) Currently meets criteria for a PTSD diagnosis, determined by the Clinician-Administered PTSD Scale-5. 3.) Engaged in at least 3 self-reported impulsive aggression acts (e.g., yelling, throwing objects, hitting objects/people) in the last month, measured by the Overt Aggression Scale. 4.) Impulsive aggression is his/her primary form of aggression, determined by having a higher Impulsive Aggression subscore than a Premeditated Aggression subscore on the Impulsive Premeditated Aggression Scale. 5.) Because aggressors are poor historians when reporting their aggression frequency, each Veteran must agree to allow an independent aggression rater (a person with whom the Veteran has a long-standing, close personal relationship and has in-person interaction most of the days of the week; ) verify the number of aggressive acts, using the Overt Aggression Scale. 6.) No psychotropic medication change for six weeks prior to the assessment and agreement not to ask for a medication change for the duration of the study.

Exclusion criteria: Veterans who meet the following criteria will be excluded: 1.) Previously began PE or CPT. 2.) Is currently suicidal with intent of self-harm in the last week. 3.) Is currently homicidal with plans to hurt a specific person. 4.) Is unable to complete self-report measures. 5.) Does not have an independent aggression rater. 6.) Has severe alcohol consumption patterns (Alcohol Use Disorders Identification Test), severe drug use consumption patterns (Drug Use Disorders Identification Test), active psychosis, or mania (MINI). 7.) Had a psychotropic medication change within 6 weeks prior to the pretraining assessment. Veterans receiving general mental health services or non- PE or CPT psychotherapy will be allowed to participate in this study.

**7. Expected Results (Publication and Presentation Plans):** The PI plans to publish a manuscript describing the results of the pilot project after the final data are collected in 2019. Data will be presented in aggregate form, or if case studies are written, all information will be disguised with no identifying information.

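### Entry criterion 3 counts acts over a month on an OAS that covers only a week; the plan does not say how this was resolved or which OAS record anchors the pre-to-post change

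*Combined protocol and SAP*

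**What the plan says.** - **The entry rule.** Section 6, inclusion criterion 3, requires at least 3 self-reported impulsive acts "in the last month, measured by the Overt Aggression Scale".
- **The instrument.** Section 4, Measures, item 7 b), describes one self-report OAS, "adapted for the current study to indicate frequency of each aggressive act over the past week". It covers "verbal and physical aggression against self, other, and objects", and "Aggressive acts will be summed to create a total score". No one-month version is described.
- **The deciding visit.** Section 4, Screening Procedures: "Veterans must then meet eligibility criteria based on the pre-training assessment". The assessment schedule shows no OAS at screening. The first is at pre-training.
- **The phone screen.** It asks for "aggression frequency in the past month (self-reported number of aggressive acts", without naming the OAS. The same paragraph adds: "No screening data will be used as study data".
- **OAS records before training.** There are three: the pre-training assessment; tracking forms kept for about 2 weeks by Veterans already found eligible, which the Pretraining assessment procedures describe as giving a baseline; and the OAS at session 1.
- **The analysis.** Data Analysis/Statistics, Aim 2, fits a mixed model with a main effect of time to data from all sessions, with pairwise comparisons where appropriate. It does not say which early OAS record is the reference for the pre-to-post change.

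**The concern.** The rule and the instrument it names use different windows. Three or more impulsive acts in the past week also satisfy the monthly rule. A count of 0, 1 or 2 leaves the monthly total unknown, so staff needed a workaround, and the documents do not say which.

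The choice matters because the self-report OAS is listed among the primary outcomes and the design has no control group.

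- If the threshold was applied to the weekly form, Veterans were selected for a high value of the score later used as the pre-training outcome. Such scores tend to fall at the next measurement without any treatment effect.
- If pre-training recall was stretched to a month, a monthly total would be compared with later weekly totals.
- If the phone count was used, neither distortion arises in this form, but the named instrument and deciding visit were not followed.

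The first two effects touch only comparisons that use the pre-training OAS, so it matters which record anchors the change.

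**Working it through.** The plan gives no OAS rate, standard deviation or effect size, so there is no stated figure to reproduce. The inputs from the documents are the threshold (3 acts), the two windows (a month, a week) and the OAS schedule. Everything else below is an assumption shown over a range. All acts are treated as impulsive and a month as 30 days.

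**Step 1. Scale of the mismatch.** Three acts in 30 days is 3 × 7/30 = 0.7 per week. Three acts in 7 days is 3 × 30/7 = 12.9 per 30 days, about 4.3 times the written threshold.

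**Step 2. Who falls in the gap, for a fixed monthly count.** If m acts are spread independently and evenly over 30 days, the number in the last 7 days is Binomial(m, 7/30). The chance of 0 to 2 is:

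| Acts in the month | 3 | 6 | 12 | 20 | 30 |
|---|---|---|---|---|---|
| Shows 0-2 on the weekly form | 98.7% | 85.6% | 44.4% | 12.2% | 1.7% |

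**Step 3. A population model.** Let each Veteran's weekly rate follow a gamma distribution with mean μ and shape k (0.7 to 2), stable over time, with Poisson counts given the rate and no change in behaviour. Let X be the weekly count.

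- Share of monthly-eligible Veterans with 0-2 acts in the week = 1 − P(X ≥ 3) / P(month ≥ 3).
- Expected weekly count at a later visit, given X, = (k + X) / (k/μ + 1).
- Apparent fall if the threshold is applied to the weekly form = 1 − E[later | X ≥ 3] / E[X | X ≥ 3].

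Worked case, μ = 2 and k = 1. P(X ≥ 3) = (2/3)³ = 0.296. The monthly mean is 2 × 30/7 = 8.57, so P(month ≥ 3) = (8.57/9.57)³ = 0.718, and the share is 1 − 0.296/0.718 = 0.587. E[X | X ≥ 3] = 3 + 2 = 5.00, and the later mean is (1 + 5)/(1/2 + 1) = 4.00. The apparent fall is 1 − 4.00/5.00 = 20%.

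Over k = 0.7 to 2:

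| Mean acts per week | Eligible by month, 0-2 in the week | Apparent fall, weekly threshold |
|---|---|---|
| 1 | 73-82% | 32-48% |
| 2 | 56-63% | 16-27% |
| 4 | 37-40% | 7-11% |
| 8 | 17-26% | about 3% |
| 12 | 9-20% | 1-2% |

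**Step 4. The alternatives, same model.**

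- Past-month rule, with the last 7 of the 30 days as baseline: the apparent fall is at most about 10% (mean of 1) and about 1% or less from a mean of 4 upward.
- Recall stretched to a month at pre-training only, totals not rescaled: a fall of 77-79%. Nearly all of it is the change of window, 1 − 7/30 = 76.7%.
- Session 1 OAS as baseline, weekly threshold: about 0%, because that record played no part in selection. If individual rates drift between visits, some of the effect could remain.

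**The case against.** Several points on the other side stand.

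- **The phone screen collects a past-month count.** It would be too strong to say that a Veteran with 0-2 acts in the week could not be classified by any means. The gap concerns the instrument and visit the protocol names. The sentence keeping screening data out of the study data most naturally concerns outcomes and does not by itself bar using that count for eligibility.
- **The mixed model uses all sessions and needs no single baseline.** A reader might infer that Aim 2 cannot be analysed as written. It can, and session 1 against post-training may already be among the pairwise comparisons. What is missing is a statement of which contrast carries the pre-to-post claim.
- **The harm is conditional and shrinks at higher rates.** No text says that the weekly threshold or a stretched recall was used. This sample is chosen for aggression and the OAS counts verbal acts, so 8 or 12 acts per week is plausible, and the artefact is then 3% or less.
- **Aim 2 does not rest on this score alone.** The IPAS impulsive subscale, the DERS and the independent rater's OAS are also collected. A largely descriptive open pilot cannot support a causal claim in any case. This lowers the severity, but the self-report OAS is still listed as a primary outcome.

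A reader might also take the payment text, "If he is eligible for the study based on screening questions", as a rival eligibility rule. It is payment wording, and can simply mean the questions asked at the assessment.

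Nor does any text say how impulsive acts are picked out on the OAS. That is minor: criterion 3 gives examples that fit the form, and criterion 4 uses the IPAS to require mainly impulsive aggression.

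**Conclusion.** The concern holds as a conflict between a stated entry rule and its own instrument, with an unstated anchor for the pre-to-post OAS change. That part is plain from the text and needs no model.

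The size of any bias is not known. If the weekly form was the gate, the apparent fall with no real change runs from 32-48% at a mean of 1 act per week down to 1-2% at 12. These figures rest on assumed gamma-Poisson counts, stable individual rates, all acts counted as impulsive, and means the documents do not supply. They do not show that this trial's result is biased, because the documents do not say which workaround was used.

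It should be fixed, at the lower end of that grade: the consequence may be small, but nothing in an uncontrolled design would reveal it, and the data for a check are already collected.

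**What to change.** 1. Reconcile Screening Procedures, the OAS description in Measures, and inclusion criterion 3, so that one instrument, one recall window and one visit decide the criterion. A line on how impulsive acts are counted would settle the minor point.
2. For Veterans already enrolled, disclose which window and source were used. The Aim 2 text is partly in the past tense, so this may be all that remains possible for them on eligibility.
3. Keep one OAS recall window at every outcome time point in the assessment schedule.
4. In Data Analysis/Statistics, name the OAS record that anchors the pre-to-post change. Also report the change to post-training from a record made after eligibility and before training (the tracking forms or the session 1 OAS), using the pairwise comparisons already planned.

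The cost is a wording change, one disclosure and one extra comparison on data already collected. The downside is that the fall from the later baseline may be smaller than the fall from the pre-training assessment.

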**9: Potential Risk:**

Category 1: Research not involving greater than minimum risk.

Potential risks include the 1.) loss of confidentiality including having to report child or elder abuse and 2.) temporary increase in anxiety or worry. 1.) The risk of losing confidentiality is minimal and will be managed by storing personally identifying information in a locked cabinet, using random subject numbers to identify the patient data in paper and electronic form, and not including personally identifiable information in databases. Limitations to confidentiality include situations wherein the patient poses a serious danger to self or others, a medical emergency occurs, or there is cause to believe that a child, older person, or disabled person is being abused, neglected, or exploited. These exceptions to confidentiality are listed on the consent form. The risk will be made explicit to the

patients prior to completing the questionnaires. Additionally, this is consistent with routine clinical practice and state laws. Often Veterans bring in their partners to PTSD treatment sessions and the same reporting laws apply in clinical practice and research.

2.) Veterans will be asked about how they are currently coping with emotional experiences. The assessments and training are already used as routine clinical practice within the VA system, with a difference being the training is delivered in a condensed format rather than the tradition 8-12 sessions. With all psychological treatments and assessments, the procedures may cause a temporary mild increase in worry, anxiety, or other emotions. The goal of the treatment is to teach participants more adaptive ways of coping, and any such increases in emotions are expected to be temporary. All patients will have the opportunity to terminate the assessment or therapy at any time. Further treatment resources will be made available, including the 24-hour Emergency Room, treatment through mental health, and the Veteran suicide hotline number. No physical risk is foreseen.

**10. Any experimental procedures:** Research has shown that emotion regulation skills can help people manage their emotions and daily stress and these skills may also help you manage your aggression. Emotion regulation treatments are already provided in the VA system and are not experimental. However, the condensed treatment format (3 sessions instead of 8-12) has not been tested before and is not currently part of standard VA practice.

#### **11: Potential Benefits:**

Potential benefits to the Veteran.

Emotion dysregulation related to PTSD can lead to aggression and is a huge barrier for OIF/OEF/OND Veterans adjusting back to civilian life. The legal, interpersonal, social, and psychological consequences of emotion dysregulation and aggression are far-reaching and are a constant strain on individuals, families, and society. The intervention teaches Veterans how to better manage emotions and his aggression. The Veteran may feel better in his daily life after learning these skills. Additionally, a goal of the study is to decrease aggression, which has interpersonal, legal, and financial consequences. If the study assists Veterans in being able to control aggression, improved psychosocial functioning may be the result. However, the participant may obtain no benefit from participating.

Potential benefits to society of the planned work.

Expanding the understanding of what treatments work to reduce aggression is imperative and this condensed treatment may offer Veterans some relief from their emotion dysregulation and impulsive aggression in a shorter time frame than traditional anger management treatments. Decreases in aggression not only benefit the Veteran, but also the Veteran's family and community. The treatment may also benefit the VA because of the decrease in provider time required to deliver the training. The VA system is already taxed with serving the increasing number of returning Veterans and this may help reduce that challenge.

Risk-to-benefit ratio.

This proposed work has a favorable risk-to-benefit ratio because there are many potential benefits to the participants and society which include better emotion regulation skills, reducing aggression, and

increasing knowledge about what helps Veterans reduce aggression. Additionally, Veterans may experience improvements in emotion regulation skills after 3 sessions, as compared to traditional emotion regulation treatments, which are 8-12 sessions. The VA may also benefit from the condensed format of the training. The possible risks are minimal and typically transient and are no more than experienced during routine clinical practice.

---

## **12. Human Subjects considerations:**

Four forms are being requested as part of this study: A waiver of informed consent, a waiver of HIPPA authorization (for screening), an informed consent, and a HIPPA authorization. In order to screen participants, waivers of informed consent and HIPPA authorization are requested to allow the research staff to open the medical records of veterans who have been referred to the PTSD clinic. This will allow the research staff to see if the Veteran appears appropriate for the study before contacting the Veteran. If the Veteran likely meets study criteria, research staff will send a letter describing the study to the Veteran which will provide a number the Veteran can call for more information or to opt-out of the study. The letter will explain that the research staff will call the Veteran in two weeks if they do not receive an opt-out call. After two weeks, study staff will call the Veteran, explain the study, and receive verbal consent to continue the telephone call. Research staff will then conduct the phone screen.

Veterans who are eligible based on the phone screen will be scheduled for an in-person, pretraining informed consent session which will take place in a private office. Research staff will explain the study to the Veteran including the risks and benefits, that participant is voluntary and will in no way affect his/her treatment, and that s/he can withdraw from the study at any time without explaining why. The research staff will answer all questions. If the Veteran would like to take home the informed consent form and further consider if he would like to participate, another session will be scheduled for the pre-training assessment session.

